### OR

• Reduction of ≥ 4 RBC transfusions/8 weeks

in comparison to pre-treatment values and lasting at least 8 weeks. According to IWG criteria, HI is measured in patients with pre-treatment hemoglobin levels of less than 11 g/dL or RBC transfusion dependence. Pre-treatment hemoglobin levels must not be influenced by transfusions (no transfusion received for at least one week preceding the hemoglobin measurement). The last hemoglobin value measured prior to randomization will be used as the pre-treatment value. (If 2 pre-treatment Hemoglobin values are available and each is at least 7 days after any transfusion, an average of the 2 values will be used to determine the pre-treatment hemoglobin value). Similarly, measurements after randomization influenced by preceding transfusions within one week will not contribute to the response criteria. All RBC

transfusions regardless of pre-transfusion hemoglobin level will count in the RBC transfusion response evaluation.

All episodes of HI in the patient will be considered.

The percentage of responders will be reported for the two treatment groups. The equality of proportions in the two groups will be analyzed by an exploratory test. Further details will be described in the RAP.

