2.7.1.1 Hematologic improvement

Hematologic improvement (HI) in terms of erythroid response during treatment will be assessed based on International Working Group (IWG) criteria (Cheson 2006).

The variable used in the analysis of HI will be the proportion of patients who satisfy the erythroid response criteria; namely,

• Hemoglobin increased $\geq 1.5 \text{ g/dL}$

OR

Reduction of ≥ 4 units of RBC transfusions over 8 weeks, in comparison to 8 weeks' pretreatment values, and lasting at least 8 weeks.

For purposes of calculating the reduction in transfusions component of this endpoint, a transfusion unit is defined as 185 mL of PRBC (Cohen Glimm Porter 2008). According to IWG criteria, HI is measured in patients with pre-treatment hemoglobin levels of less than 11 g/dL or RBC transfusion dependence. The definition of transfusion dependency is based on IWG criteria (Cheson 2006). All patients included in this study are transfusion dependent. In order to measure hemoglobin increase, the last hemoglobin value measured prior to randomization will be used as the pretreated value. If 2 pre-treated (prior randomization) hemoglobin values are available and each is at least 7 days after any transfusion, an average of the 2 values will be used to determine the pre-treatment hemoglobin level. All RBC transfusions regardless of pre-transfusion hemoglobin level, will count in the RBC transfusion response criteria. If any pre-treatment hemoglobin value or transfusion history over 8-week period cannot be determined, they will not be a part of risk set and will not be included in the percentage calculation.

All episodes of HI in the patient will be considered.

The percentage of responders will be summarized for the two treatment groups and $100(1-\alpha)\%$ confidence intervals with α of 0.05 will be provided. The 95% confidence limits for the difference of two proportions will be derived by the Wilson score test (see Section 5.5.3).

Overall survival

Overall survival (OS) will be evaluated in patients treated with either deferasirox or placebo. The variable used in the analysis of overall survival is time to death measured in days. It is defined as date of death (irrespective of cause) minus date of randomization plus 1.

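### SAP 2.7.1.1 omits the protocol's two one-week post-transfusion hemoglobin exclusions for hematologic improvement, and SAP section 4 declares no change

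*SAP*

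**What the plan says.** Both documents define an HI responder by a hemoglobin rise of at least 1.5 g/dL or a fall of at least 4 red-cell transfusions (units, in the SAP) over 8 weeks.

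Protocol 10.5.1.1 then limits which hemoglobin values may be used. Before treatment the requirement is "no transfusion received for at least one week preceding the hemoglobin measurement". After randomization, "measurements after randomization influenced by preceding transfusions within one week will not contribute to the response criteria". The duration clause, "in comparison to pre-treatment values and lasting at least 8 weeks", follows both criteria.

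SAP 2.7.1.1 says that "the last hemoglobin value measured prior to randomization will be used as the pretreated value". It adds an averaging rule that opens "If 2 pre-treated (prior randomization) hemoglobin values are available and each is at least 7 days after any transfusion". It then says of patients whose pre-treatment hemoglobin or 8-week transfusion history cannot be determined that "they will not be a part of risk set and will not be included in the percentage calculation". As printed, its duration wording, "pretreatment values, and lasting at least 8 weeks", stands in the transfusion criterion.

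SAP section 4 lists one change to the protocol's analyses, on thrombocytopenia and neutropenia. The SAP version log, under Amendment 1, describes the HI edit as a clarification.

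**The concern.** The SAP repeats the sentences on either side of the two exclusions and leaves the exclusions out. Someone programming HI from the SAP alone would accept a baseline hemoglobin drawn the day after a transfusion, and would accept any on-study hemoglobin.

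This matters in this population because the SAP itself states: "All patients included in this study are transfusion dependent". Hemoglobin drawn soon after a transfusion is therefore foreseeable, and the protocol provided for it. If the SAP is followed as printed, the responder proportion reported is not the one the protocol defines. A raised baseline makes a true hemoglobin response harder to see, and raised on-study values can pass for part of one.

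**Working it through.** The plan gives no HI response rate, power or other figure to reproduce. The check is a comparison of protocol 10.5.1.1 with SAP 2.7.1.1.

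| Rule on usable hemoglobin values | Protocol 10.5.1.1 | SAP 2.7.1.1 |
|---|---|---|
| Pre-treatment value needs a transfusion-free week before it | Yes, unconditional | Absent |
| Last value before randomization is used | Yes | Yes |
| Two pre-treatment values are averaged if each is at least 7 days after a transfusion | Yes | Yes |
| Post-randomization value within a week after a transfusion is not used | Yes | Absent |

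**What the surviving 7-day wording does.** In the SAP it only switches averaging on. If one of two values fails the 7-day test, averaging is off and the printed rule returns to the last value, which may be the one that failed. It says nothing about values after randomization.

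**Direction of error.** Let x be the amount (g/dL) by which a transfusion raises the baseline, and y the amount by which one raises an on-study value.
- Observed rise = true rise + y − x.
- The criterion needs an observed rise of at least 1.5, so the true rise needed is 1.5 + x − y.
- With only the baseline raised it is 1.5 + x (a response can be hidden). With only the on-study value raised it is 1.5 − y (a value can pass too easily).

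The documents give no x or y, and none is assumed.

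**How often a value could fall in the window.** This is not in the documents, so what follows is an assumption with a range. Suppose draws are timed independently of transfusions and the 7-day windows do not overlap. With k transfusion days per 8 weeks, the share of values inside a window is 7k/56:
- k = 1: 7/56 = 12.5%
- k = 2: 14/56 = 25%
- k = 4: 28/56 = 50%

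A patient needs at least 4 units per 8 weeks at the start to show a 4-unit reduction. That is k = 2 if given two at a time and k = 4 if given singly. The true share could be well below this range if draws are timed around transfusions. These are shares of hemoglobin values, not of patients or responders.

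**Denominator.** Take a transfusion-dependent patient whose only pre-treatment hemoglobin values fall within a week after a transfusion.
- Protocol: no valid hemoglobin baseline. HI is still measurable, because eligibility for the assessment is hemoglobin below 11 g/dL or transfusion dependence.
- SAP as printed: the patient keeps a baseline and stays in.
- SAP with the exclusions restored and nothing else changed: the risk-set sentence removes the patient, even if the transfusion criterion could be assessed.

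**The case against.** The strongest reply is that the SAP omits the exclusions without contradicting them. SAP section 1 says it implements the analysis in the protocol, SAP 2.1 points to protocol section 10, and SAP 2.7.1.1 cites the IWG criteria. The protocol carries the same last-value and averaging sentences with the exclusions beside them. If the exclusions are inherited, section 4 has nothing to declare. Part of this stands: a reader might infer that the sponsor changed the definition, and the documents do not show that. But SAP 2.1 refers to protocol section 10 as detailed in the SAP, and the SAP then gives an explicit last-value rule without the condition. The protocol leaves further details to the RAP, and dropping a stated exclusion is not a further detail. Inheritance is possible but not stated.

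Three stronger readings are tempting and should not be drawn.
- *One post-transfusion value on study makes a responder.* With visits about every 4 weeks, that follows only if the 8-week duration does not apply to the hemoglobin criterion. The SAP's printed layout suggests this, but the second criterion appears to have lost its bullet in extraction, so the layout is weak evidence.
- *Most patients have a single pre-treatment value, so the fallback usually operates.* Table 7-2 schedules one blood count before randomization, at Screening Visit 1. However, Table 7-1 footnote 1 and the protocol section on transfusion requirements also collect hemoglobin for the 6 months before. More values may exist.
- *Timing rules already protect hemoglobin.* The instruction to draw before a transfusion or two weeks after is written for ferritin only. It may keep shared draws outside the window, but it is not a hemoglobin rule.

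The objection that simply restoring the exclusions would remove assessable patients is correct, and the fix below allows for it.

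**Conclusion.** The discrepancy is real and undeclared: two of the four protocol rules on usable hemoglobin values, as tallied above, are missing from the SAP. As printed, the SAP yields a responder variable that can differ from the protocol's, with error possible in both directions. How many patients or responders would change cannot be determined from the documents.

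Severity is low. HI is an exploratory secondary endpoint, SAP 2.7.2 tests no hypothesis for secondary endpoints, and event-free survival is unaffected. A reader might infer a bias in favour of deferasirox. Nothing in the documents shows that post-transfusion draws would differ between arms in this double-blind trial. The conclusion assumes that the analysis is programmed from the SAP text and that no document outside the two reviewed supplies the missing filter.

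**What to change.** In SAP 2.7.1.1:

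1. Restore both exclusion sentences from protocol 10.5.1.1, covering hemoglobin before and after randomization. If the sponsor meant to drop either, declare and justify that in SAP section 4.
2. Amend the risk-set sentence so that a transfusion-dependent patient without a qualifying pre-treatment hemoglobin stays in the denominator and is assessed on the transfusion criterion, provided the 8-week transfusion history is available.
3. Check the source layout and confirm that the 8-week duration covers both criteria, as in the protocol.

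The cost is a few sentences and a small amount of programming, mainly a date check between hemoglobin and transfusion records that are already collected. The downside is fewer evaluable hemoglobin values.

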2.7 Analysis of secondary efficacy objective(s)

2.7.1 Secondary efficacy endpoints

All analyses of secondary efficacy endpoints will be based on the FAS.

If applicable, nominal significance levels will be set to one-sided alpha = 0.025; all confidence intervals will be two-sided using an ordinary confidence level of 95%.

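### The hematologic improvement rule in SAP 2.7.1.1 drops a patient when either baseline item is missing, although the endpoint can be met on either route alone

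*SAP*

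**What the plan says.** SAP 2.7.1.1 sets the endpoint as a responder proportion: "The variable used in the analysis of HI will be the proportion of patients who satisfy the erythroid response criteria". A patient responds by a hemoglobin increase of at least 1.5 g/dL, or by a reduction of at least 4 "units of RBC transfusions over 8 weeks, in comparison to 8 weeks" before treatment. On who can be assessed, the section says that "HI is measured in patients with pre-treatment hemoglobin levels of less than 11 g/dL or RBC transfusion dependence", and adds: "All patients included in this study are transfusion dependent".

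The exclusion follows in the same paragraph: "If any pre-treatment hemoglobin value or transfusion history over 8-week period cannot be determined, they will not be a part of risk set". The sentence goes on to say that such patients "will not be included in the percentage calculation".

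The section opening, SAP 2.7.1, states: "All analyses of secondary efficacy endpoints will be based on the FAS". SAP 2.2.1 defines the FAS as all randomized patients.

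Protocol 10.5.1.1 contains no exclusion for a missing baseline item. It does restrict which values count: "Pre-treatment hemoglobin levels must not be influenced by transfusions", meaning no transfusion in the preceding week. It leaves further HI detail to the analysis plan.

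**The concern.** The endpoint joins its two routes with OR, and so does the eligibility condition. The exclusion also uses OR, but in the opposite sense: a gap in either item removes the patient from both numerator and denominator. A patient can therefore be set aside for lacking data that the other route does not need.

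The SAP regards every patient as transfusion dependent, so every patient qualifies for HI without a baseline hemoglobin. A missing hemoglobin should then close one route, not remove the patient.

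At stake is what the percentages describe. Under the rule they describe patients with both items complete, not the FAS. The interval for the difference is wider than it need be, and any transfusion response in an excluded patient goes uncounted.

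**Working it through.** **No plan figure to reproduce.** The documents give no HI rate, missingness rate or evaluable number. The sample size of 210 rests on feasibility (Protocol 10.7, SAP 3), and no power was calculated for secondary variables (Protocol 10.8).

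**Step 1: logic at baseline.**

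| Pre-treatment hemoglobin | 8-week transfusion history | Routes assessable | SAP rule |
|---|---|---|---|
| available | available | both | kept |
| missing | available | transfusion | dropped |
| available | missing | hemoglobin, if the value can be verified as transfusion-free | dropped |
| missing | missing | none | dropped |

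Only the last row is a patient who clearly cannot be assessed. The second row is the firm part of the point. The third is conditional, because confirming that no transfusion fell in the preceding week needs transfusion dates.

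**Step 2: how many, under assumed rates.** Let h be the share missing hemoglobin and t the share missing transfusion history. Both are assumed, and assumed independent. With N = 210:

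- dropped by the SAP rule = N × [1 − (1 − h)(1 − t)]
- transfusion route assessable but dropped = N × h(1 − t)
- hemoglobin only, dropped = N × (1 − h)t
- neither item = N × ht

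| h | t | Dropped by rule | Transfusion route assessable | Hemoglobin only | Neither |
|---|---|---|---|---|---|
| 5% | 0% | 10.5 | 10.5 | 0 | 0 |
| 10% | 5% | 30.5 | 20.0 | 9.5 | 1.1 |
| 20% | 5% | 50.4 | 39.9 | 8.4 | 2.1 |

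For example, at h = 10% and t = 5%: 210 × (1 − 0.90 × 0.95) = 210 × 0.145 = 30.5, and 210 × 0.10 × 0.95 = 20.0. Excluding only patients with neither item would drop about 1 patient instead of about 30.

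**Step 3: precision.** The 2:1 allocation gives 140 and 70. Assume 20% response in both arms and a fraction f lost equally from each. The Wald 95% half-width is

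1.96 × √[0.20 × 0.80 × (1/(140(1 − f)) + 1/(70(1 − f)))]

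At f = 0 this is 1.96 × √(0.16 × 0.021429) = 1.96 × 0.05855 = 11.5 points. Other values follow by dividing by √(1 − f):

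| f | Patients left | Half-width (points) |
|---|---|---|
| 0 | 140 / 70 | 11.5 |
| 5% | 133 / 66.5 | 11.8 |
| 10% | 126 / 63 | 12.1 |
| 20% | 112 / 56 | 12.8 |

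SAP 5.5.3 specifies Wilson limits with continuity correction, so a check on that interval is useful. With 42/140 against 14/70 responders (30% and 20%, chosen for illustration), the difference is 10.0 points (95% CI −3.7 to 21.8), a width of 25.5. After a near-random 20% loss, 34/112 against 11/56 gives 10.7 points (−4.8 to 23.8), a width of 28.6. The ratio is 28.6/25.5 = 1.12, matching 1/√0.80 = 1.12.

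**The case against.** **Delegation.** Protocol 10.5.1.1 hands HI detail to the analysis plan, and SAP 2.1.1 allows percentages on the relevant population or subgroup. An evaluability rule can be seen as that delegated detail. This stands against calling it an undeclared protocol change merely because SAP 4 does not list it. It does not reconcile the rule with the FAS statement in SAP 2.7.1.

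**Small numbers.** Protocol 7.5.5 requires six months of transfusion records with associated hemoglobin values before randomization, and says blood counts must be available for that period. Table 7-2 adds hematology at Screening Visit 1. SAP 2.7.1.1 takes the last pre-randomization hemoglobin and states the 7-day condition only for averaging two values. On that wording nearly every patient may have a determinable value. This largely stands. A reader might infer that the rule shifts the population away from heavily transfused patients. That follows only if the protocol's transfusion-free week is also applied to a single value, which the SAP does not say.

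**Bias between arms.** A reader might infer that the treatment contrast is distorted. Hand-picked unequal responder losses can move the estimate either way, but the documents support no such pattern. Both items are fixed before randomization, so exclusion cannot depend on the assigned treatment.

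**On-treatment reading.** The 8-week phrase does not itself say pre-treatment, so a reader might think it also removes early discontinuers. That reading is strained. The phrase is paired with a pre-treatment hemoglobin, the comparator in the same section is the 8 weeks before treatment, and history is a baseline term. The documents give no discontinuation rates by arm.

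**Route-by-route reading.** The word for those removed has no clear antecedent, so exclusion per route is conceivable. Removal from the percentage points to exclusion of the patient.

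**Conclusion.** The rule does not fit the endpoint. It removes patients who can be assessed on the transfusion route and, less certainly, some assessable on the hemoglobin route. The HI percentages then fall short of the FAS basis that the SAP states for them.

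The consequence is lost precision and generalizability. At an assumed 5% to 20% loss, the half-width rises by 0.3 to 1.3 points from 11.5. That rests on 20% response in both arms, equal loss and a Wald approximation. The actual loss is not given and may be below this range. Any count of discarded responders would be conjecture.

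HI is a secondary endpoint without power or a confirmatory test, and the primary analysis is unaffected. The point is worth acting on because the correction is cheap and the sentence needs clarifying on any reading.

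**What to change.** Replace the exclusion sentence in SAP 2.7.1.1 with:

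> A patient is excluded from the HI denominator only if neither route can be evaluated at baseline; a patient with one evaluable route is classified on that route.

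In addition:

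- State that the 8-week period is the pre-treatment period.
- Report the number excluded by arm and by missing item.
- Add a sensitivity analysis with all FAS patients in the denominator and non-evaluable patients counted as non-responders.

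The cost is one SAP sentence with short additions and a small programming change. The drawback is that patients evaluable on one route have fewer ways to respond, so the percentage may be slightly lower. This matters most for lightly transfused patients without a usable hemoglobin. Entry requires an anticipated 8 units a year, which is 8 × 8/52 = 1.2 units per 8 weeks, and a patient near that level cannot show a reduction of 4 units. The counts by missing item will show how many patients were classified on one route if they are tabulated for retained patients as well as excluded ones.

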2.5.2.2 Estimation of survival functions for event-free survival

A graphical estimate of the survival function for each treatment group will be obtained separately by the Kaplan-Meier (KM) product-limit method as implemented in SAS PROC LIFETEST.

If available, median survival for each treatment group will be obtained by SAS PROC LIFETEST along with 2-sided 95% confidence intervals calculated using the method of (Brookmeyer and Crowley 1982).

KM estimates with 2-sided 95% confidence intervals at days 364, 728, 1092 and 1456 will be provided. The confidence intervals will be constructed using Greenwood's formula (Collett 1994) for the standard error of the Kaplan-Meier estimate.

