2.5.3.1 Worsening of cardiac function

For the analysis of worsening of cardiac function, patients who have not experienced a worsening of cardiac function will be censored at the last date when echocardiography results are available.

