- Point estimate and two-sided 95% confidence interval for the adjusted HR from a Cox proportional hazard regression model stratified for the randomization factors with adjustment for demographic or baseline characteristics of clinical interest. The adjustment will be made for age (≥65 vs < 65), Asian vs non-Asian, MDS risk group (low vs intermediate).
- Statistical analyses based on the PPS instead of the FAS.

Supportive analyses include:

- KM curves by treatment and unadjusted HR (point estimate and two-sided 95% confidence interval) for each of the strata defined by the randomization factors.
- KM curves by treatment and unadjusted HR (point estimate and two-sided 95% confidence interval) for each component of event-free survival (overall survival is also a secondary efficacy endpoint, see Section 2.7.1.1).
- Number of deaths and non-fatal events adjudicated by the endpoint adjudication committee

- Primary endpoint analyses will be repeated for the FAS excluding patients from one site due to data integrity issue. The time to event analyses will be performed and will include.
 - Stratified log-rank test and Cox-regression model for event-free survival
 - Overall summary of event free survival

These patients will be excluded from per-protocol set for the sensitivity analyses.

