Censoring is described in Section 2.7.3.1. The estimation of survival functions and the Cox model to estimate the HR are defined in Section 2.5.2.2 and Section 2.5.2.3. An exploratory statistical test will be performed analogously to the description in Section 2.5.2.4.

The Kaplan-Meier curves, medians, and Kaplan-Meier estimates with 95% confidence intervals at specific time points will also be displayed by treatment and stratum.

In Kaplan-Meier plots, statistics such as p-value, hazard ratio, etc. will also be displayed. Note that only nominal p-values are provided with no statistical interpretation.

Survival information will be listed. The listing will include if patients survived (Yes/No), last contact date, study day, date of death if not survived and principal cause of death.

Unless otherwise specified, all time-to-event analysis will be analyzed in a similar fashion.

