2.7.3.2 Disease progression to MDS

For the analysis of time to disease progression (see Section 2.7.1.4), patients who did not experience an MDS progression will be censored at the last contact date.

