2.8 Safety analyses

As stated in the protocol (Section 3.2), one of the secondary objectives was to evaluate safety, in particular to assess the levels of increased risk for pre-specified adverse events (renal dysfunction, neutropenia, thrombocytopenia, gastrointestinal bleeding, and laboratory abnormalities) that would be clinically unacceptable in the context of the level of benefit that is likely to be provided by iron chelation using deferasirox in MDS patients with iron overload.

Endpoints for the secondary safety objectives are as follows:

- 1. Proportion of patients with significant renal dysfunction
- 2. Proportion of patients with newly occurring moderate or severe neutropenia or thrombocytopenia
- 3. Proportion of patients with major gastrointestinal bleeding
- 4. Time to study drug discontinuation due to an adverse event or laboratory abnormality
- 5. Incidence of other adverse events and laboratory abnormalities

The first four endpoints are defined and evaluated as follows:

Proportion of patients with significant renal dysfunction defined as serum creatinine ≥ 2 times ULN at two consecutive assessments (at least 7 days apart) Frequency tables by treatment group will be prepared along with a two-sided 95% confidence interval for evaluation of DFX in contrast to placebo. Results will also be

Endpoint	Analysis
Proportion of patients with newly occurring neutropenia (absolute neutrophils count <1.0×10 ⁹ /L) or thrombocytopenia (platelets <50×10 ⁹ /L)	provided for annual time intervals.
Proportion of patients with major gastrointestinal bleeding.	
Time to study drug discontinuation due to an AE or laboratory abnormality, more specifically date of study drug discontinuation due to an AE or laboratory abnormality minus date of randomization plus 1.	The time-to-event analysis follows the description given in Section 2.5.2.2 The statistical test will be exploratory in nature. For the analysis of time from randomization to study drug discontinuation due to an AE or laboratory abnormality (see Section 2.8.3), patients who did not discontinue study medication due to an AE or laboratory abnormality will be censored at the date of study drug discontinuation.

Proportion of patients with moderate or severe anemia will be analyzed like newly occurring neutropenia.

Other analyses and other safety data (ocular and auditory examinations, electrocardiogram, and vital signs) will be also considered.

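### Kaplan-Meier displays of the non-fatal endpoints and of AE-related discontinuation overstate absolute risk, because death and other competing exits are left to the censoring rules

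*SAP*

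**What the plan says.** SAP 2.7.1.1, under overall survival, specifies the display: "The Kaplan-Meier curves, medians, and Kaplan-Meier estimates with 95% confidence intervals at specific time points will also be displayed by treatment and stratum". It then extends the approach: "Unless otherwise specified, all time-to-event analysis will be analyzed in a similar fashion". SAP 2.5.2.2 supplies the detail, namely medians and "KM estimates with 2-sided 95% confidence intervals at days 364, 728, 1092 and 1456". The SAP texts on disease progression, LVIDD, LVISD, ferritin doubling (within 2.7.1) and AE or laboratory discontinuation (2.8) all refer to 2.5.2.2. SAP 2.5.4 separately asks for KM curves and an unadjusted hazard ratio "for each component of event-free survival".

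The censoring rules make no separate provision for death:

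- Cardiac worsening (SAP 2.5.3.1): "patients who have not experienced a worsening of cardiac function will be censored at the last date when echocardiography results are available". Liver function impairment, LVIDD, LVISD and ferritin likewise use the last relevant assessment.
- Heart-failure hospitalization, cirrhosis and AML use the last contact date, and so does disease progression (SAP 2.7.3.2): "patients who did not experience an MDS progression will be censored at the last contact date".
- Patients who did not stop for an AE or laboratory abnormality "will be censored at the date of study drug discontinuation" (SAP 2.8). The stopping reasons in Protocol 6.7.6.1 include death, disease progression and withdrawal of consent, but also completion per protocol and termination by the sponsor.

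Neither document mentions competing risks or cumulative incidence. The IPCW or RPSFT analysis in SAP 5.5.4 is optional and concerns only switching of chelator before an EFS event.

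**The concern.** A patient who dies cannot later progress to AML or double ferritin, and a patient who has stopped drug for another reason cannot later stop it for an AE. Treating such exits as censoring assumes that those patients remain exposed to the event like everyone still followed. The complement of the KM curve then describes a setting in which the competing exit does not happen. It is not the proportion of randomized patients who have the event by a given day, and it can only equal or exceed that proportion.

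This matters more here than in a confirmatory trial. The plan is descriptive, with no confirmatory test, so curves and fixed-time estimates are part of what readers will take away. The safety objective (Protocol 3.2, SAP 2.8) weighs added risk against likely benefit, which calls for absolute risks. If mortality or other discontinuation differs between arms, the distortion differs too, and a between-arm contrast read off the curves is affected.

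**Working it through.** There is no planned figure to reproduce. The 210 patients are a feasibility number, and neither document gives event or exit rates for these endpoints.

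**Inputs**

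- Time points: days 364, 728, 1092 and 1456 (SAP 2.5.2.2). One month is 30.4375 days (SAP 2.1.2.7), so day 1092 is 1092/30.4375 = 35.88 months.
- Death: median survival of 40, 51 and 115 months, the background figures in Protocol 1.1. They run from diagnosis in other cohorts, so they are scenarios and not predictions. Hazard c = ln 2 / median: 0.01733, 0.01359 and 0.00603 per month.
- Event rate: assumed 10% per year, so λ = -ln(0.90)/12 = 0.00878 per month. A range of 3% to 15% was also run.
- Other exits, for AE or laboratory discontinuation: assumed 15%, 25% and 40% per year, so c = 0.01354, 0.02397 and 0.04257 per month.

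**Formulas (constant hazards)**

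- Shown by the plan: 1-KM(t) = 1 - exp(-λt).
- Proportion with the event: CIF(t) = λ/(λ+c) × [1 - exp(-(λ+c)t)].

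**Day 1092, 10% per year**

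- 1-KM = 1 - exp(-0.00878 × 35.88) = 1 - exp(-0.315) = 27.0%.
- Median 40 months: CIF = 0.00878/0.02611 × [1 - exp(-0.937)] = 0.336 × 0.608 = 20.4%.
- Median 115 months: CIF = 0.00878/0.01481 × [1 - exp(-0.531)] = 0.593 × 0.412 = 24.4%.
- Other exits 40% per year: CIF = 0.00878/0.05135 × [1 - exp(-1.842)] = 0.171 × 0.842 = 14.4%.

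**All SAP time points, event rate 10% per year**

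| | Day 364 | Day 728 | Day 1092 | Day 1456 |
|---|---|---|---|---|
| 1-KM | 10.0% | 18.9% | 27.0% | 34.3% |
| CIF, median survival 40 months | 9.0% | 15.6% | 20.4% | 24.0% |
| CIF, median survival 51 months | 9.2% | 16.3% | 21.7% | 25.8% |
| CIF, median survival 115 months | 9.6% | 17.7% | 24.4% | 30.1% |
| CIF, other exits 15% per year | 9.2% | 16.3% | 21.7% | 25.8% |
| CIF, other exits 25% per year | 8.7% | 14.6% | 18.5% | 21.2% |
| CIF, other exits 40% per year | 7.8% | 12.1% | 14.4% | 15.6% |

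**Rare and early events.** At 3% per year, day 364 gives 3.0% against 2.7% with a 40-month median, a gap of 0.3 points. Day 1092 gives 8.7% against 6.5% (40 months) or 7.8% (115 months).

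**Unequal mortality.** Take the same 10% event rate in both arms and assumed median survival of 40 months in one and 60 in the other. The day-1092 cumulative incidences are 20.4% and 22.4%, while 1-KM shows 27.0% in both.

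**Simulation check.** In 2,000 simulated trials per setting, with arms of 140 and 70 and assumed administrative censoring between 3 and 8 years, KM was at or above Aalen-Johansen every time. At 10% per year and a 40-month median, the day-1092 means were 27.0% and 20.4% with 140 patients, and 26.9% and 20.3% with 70.

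**The case against.** Several counter-arguments have force.

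- **Censoring of deaths is not written down.** A reader might infer that the SAP expressly censors at death. It does not. SAP 2.1.2.4 derives the last contact date only for patients not known to have died. The SAP therefore gives no date for event-free deaths in the four analyses that use it: heart-failure hospitalization, cirrhosis, AML and disease progression. That stands. Since death is not an event there, censoring is the natural reading, and the missing date is a gap to close in any case.
- **Medians and landmarks are not expressly required for the EFS components.** A reader might infer this from the default rule. SAP 2.5.4 itself names only KM curves and hazard ratios for them, so the fixed-time point is firm only for the endpoints sent to 2.5.2.2.
- **The treatment effect measure is the hazard ratio.** SAP 2.5.2.3 says so. With death censored, it is a valid cause-specific ratio, and the log-rank test is valid in the same sense. The claim that the curves and landmark rates are the trial's result goes too far.
- **Crude counts are planned.** The plan has adjudicated events (SAP 2.5.4), AEs leading to discontinuation (2.8.1) and end-of-treatment reasons (2.3). These help, but they do not give risk at a fixed day under unequal follow-up.
- **Not every other stop competes.** Completion per protocol and termination by the sponsor are administrative. Counting them as competing events would bring in a new error.

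**Conclusion.** The point holds as a matter of estimation for the non-fatal time-to-event endpoints and for AE or laboratory discontinuation: 1-KM read as absolute risk is biased upward. The direction is certain wherever a competing exit occurs. The size is not, because it rests on assumed event and exit rates, constant hazards, and survival medians from other cohorts. At day 1092 and 10% per year, 1-KM exceeds the cumulative incidence by 2.6 to 6.6 points when death competes (27.0 - 24.4 and 27.0 - 20.4). For AE or laboratory discontinuation the excess is 5.3 to 12.6 points (27.0 - 21.7 and 27.0 - 14.4).

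A reader might infer that the primary analysis or the planned comparisons are compromised. The documents do not support that. EFS and overall survival count death as an event, and the Cox and log-rank results stand as cause-specific comparisons. The practical weight falls on AML, disease progression and AE or laboratory discontinuation. For rare components and early time points the change is a refinement.

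**What to change.** - Report Aalen-Johansen cumulative incidence by arm, at the SAP's four time points, for the non-fatal time-to-event endpoints, with death as the competing event. Start with AML, disease progression and AE or laboratory discontinuation.
- For AE or laboratory discontinuation, also count non-administrative stops as competing, for example disease progression, withdrawal of consent or an adjudicated endpoint. Keep completion per protocol, termination by the sponsor and still on drug at cut-off as ordinary censoring.
- Keep the stratified Cox model and label its hazard ratio cause-specific. Keep KM for EFS and overall survival.
- Define the date and status used for patients who die without the event. This closes the gap left by SAP 2.1.2.4.
- For echocardiographic and laboratory endpoints, state how deaths after the last assessment are handled. After the evaluation period patients have only six-monthly survival follow-up, so a death may be recorded well after the last measurement.

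No new data are needed: death dates and stopping reasons are already collected. The cost is some added SAP wording and programming, including the rule for late deaths, and the quoted rates will be smaller.
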